
To characterize CAB and RPV concentrations and population pharmacokinetics and identify important determinants of variability
	
Plasma PK parameters for CAB LA and RPV LA (when evaluable, <math>C_{\text{trough}}</math>, concentrations post dose [<math>\sim C_{\text{max}}</math>], and area under the curve [AUC])
 
Demographic parameters including, but not limited to, age, sex, race, body weight, body mass index, and relevant laboratory parameters will be evaluated as potential predictors of inter- and intra-participant variability for pharmacokinetic parameters

To assess preference for CAB LA + RPV LA every 8 weeks or CAB LA + RPV LA every 4 weeks LA compared to oral antiretroviral (ARV)
 
To assess preference for CAB LA+ RPV LA every 8 weeks compared to CAB LA + RPV LA every 4 weeks
	
Preference for CAB LA + RPV LA every 8 weeks and CAB LA + RPV LA every 4 weeks compared to oral ARV and preference for CAB LA + RPV LA every 8 weeks compared to CAB LA + RPV LA every 4 weeks will be assessed using a preference questionnaire at week 48 (or Withdrawal).

To assess patient reported health-related quality of life, treatment satisfaction, injection tolerability, and treatment acceptance.
	
Change from Baseline (Day 1) in HRQoL at Week 24, and Week 48 (or Withdrawal)
 
Change from baseline (Day 1) in total “treatment satisfaction” score, and individual item scores of the HIV Treatment Satisfaction Status Questionnaire (HIVTSQs) at Week 24, 48, and 152 (or Withdrawal)

Objectives	Endpoints
	
Change in treatment satisfaction over time using the HIV Treatment Satisfaction Change Questionnaire HIVTSQc at Week 48 (or Withdrawal).
 
Change from Week 8 in Dimension scores (“Bother of ISRs”, “Leg movement”, “Sleep”, and “Injection Acceptance”) and individual item scores assessing pain during injection, anxiety before and after injection, willingness to be injected in the future and overall satisfaction with mode of administration over time will be assessed using the Perception of iNjection questionnaire (PIN) at Weeks 8, 24, 48, and 152 (or Withdrawal)
 
Change from Baseline (Day 1) in treatment acceptance at Week 24, Week 48 and Week 152 (or Withdrawal) will be assessed using the “General acceptance” dimension of the Chronic Treatment Acceptance (ACCEPT) questionnaire

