To characterize CAB and RPV concentrations and population pharmacokinetics and identify important determinants of variability	
Plasma PK parameters for CAB LA and RPV LA (when evaluable, <math>C_{trough}</math>, concentrations post dose [<math>\sim C_{max}</math>], and area under the curve [AUC])
 
Demographic parameters including, but not limited to, age, sex, race, body weight, body mass index, and relevant laboratory parameters will be evaluated as potential predictors of inter- and intra-participant variability for pharmacokinetic parameters

To assess preference for CAB LA + RPV LA every 8 weeks or CAB LA + RPV LA every 4 weeks LA compared to oral antiretroviral (ARV)
 
To assess preference for CAB LA+ RPV LA every 8 weeks compared to CAB LA + RPV LA every 4 weeks
	Preference for CAB LA + RPV LA every 8 weeks or CAB LA + RPV LA every 4 weeks compared to oral ARV and preference for CAB LA + RPV LA every 8 weeks compared to CAB LA + RPV LA every 4 weeks will be assessed using a preference questionnaire at week 48 (or Withdrawal).
To assess patient reported health-related quality of life, treatment satisfaction, injection tolerability, and treatment acceptance.	
Change from Baseline (Day 1) in HRQoL at Week 24, and Week 48 (or Withdrawal)
 
Change from baseline (Day 1) in total “treatment satisfaction” score, and individual item scores of the HIV Treatment Satisfaction Status Questionnaire (HIVTSQs) at Week 24, 48, and 152 (or Withdrawal)
 
Change in treatment satisfaction over time using the HIV Treatment Satisfaction Change Questionnaire HIVTSQc at Week 48 (or Withdrawal).
 
Change from Week 8 in Dimension scores (“Bother of ISRs”, “Leg movement”, “Sleep”, and “Injection Acceptance”) and individual item scores assessing pain during injection, anxiety before and after injection, willingness to be injected in the future and overall satisfaction with mode of

Objectives	Endpoints
	
administration over time will be assessed using the Perception of iNjection questionnaire (PIN) at Weeks 8, 24, 48 and 152 (or Withdrawal)
 
Change from Baseline (Day 1) in treatment acceptance at Weeks 24, 48 and 152 (or Withdrawal) will be assessed using the “General acceptance” dimension of the Chronic Treatment Acceptance (ACCEPT) questionnaire

Exploratory	

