#### 4.2.2. Maintenance Phase (Day 1 up to Week 100)

[figure not shown]
There are two ways in which study participants may transition to the LA regimen, either directly from oral SOC or from Q4W dosing from ATLAS.

Table 1 and Figure 2 describe the CAB LA + RPV LA dosing regimens in ATLAS-2M based on the mode of transition.

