- r. One blood sample for CAB and RPV each to be collected at each PK timepoint. At Day 1, for participants from the ATLAS Q4W arm, PK samples are to be collected pre-dose relative to IM administration. At Week 4b, for participants randomized from SOC, Pre dose PK samples are to be collected: AFTER review of the PK diary to ensure that the samples are taken 20/28 hours after previous oral dose (diaries to be given at Day 1 or W4a); PRIOR to the final oral dose of CAB + RPV; PRIOR to the first IM injection. Trough plasma PK samples of CAB and RPV will be obtained for every pregnant woman at every study visit during the pregnancy for both Q4W and Q8W regimens. See [Appendix 11](#).
- s. Only for Participants entering CAB + RPV Oral Treatment
- t. Participants switching to CAB LA + RPV LA will take final dose of oral lead-in regimen in the clinic at the Week 4b visit and begin injections. If possible, injections should be spaced approximately 2 cm from one another and from the site of any previous injection and or any injection site reaction. Bring RPV

- LA to approximately room temperature prior to injecting. Time and location of injection (right or left) as well as needle length used will be collected in the eCRF. The first injection can be performed as soon as central lab results become available and safety parameters are reviewed.
- u. All Patient Report Questionnaires/Surveys will be administered via paper instrument (in exceptional circumstances the questionnaires could be completed via telephonic interview, please refer to COVID19 appendix for additional details) at the beginning of the visit before any other assessments are conducted and prior to administration of the eC-CSSRS. During the Maintenance phase conduct questionnaires/surveys (HAT-QoL, HIV TSQs, HIV TSQc, ACCEPT, PIN and Preference) at W48 or upon Withdrawal only if occurring at or prior to Week 48. During the Extension phase conduct questionnaires/surveys (HIV TSQs, ACCEPT, “Reason for Oral Bridging and Preference questionnaire ” and PIN) at W152 or upon Withdrawal only if occurring at or prior to Week 152
  - v. The HIV-TSQc is to be administered to all participants transitioning from ATLAS and new participants transitioning from oral SOC. For participants transitioning from ATLAS, the version of the HIV-TSQc instrument to be administered will be based on the initial randomization arm at ATLAS Day 1.

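### The HIVTSQs, ACCEPT and PIN endpoints call for a value at Week 152 or at withdrawal, but the schedule collects none at Maintenance Phase withdrawals after Week 48

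*Protocol*

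**What the plan says.** Protocol Section 3 sets the satisfaction endpoint as the change in total and "individual item scores of the HIV Treatment Satisfaction Status Questionnaire (HIVTSQs) at Week 24, 48, and 152 (or Withdrawal". It sets the injection-perception endpoint by "questionnaire (PIN) at Weeks 8, 24, 48 and 152 (or Withdrawal", and the acceptance endpoint as the change "in treatment acceptance at Weeks 24, 48 and 152 (or Withdrawal) will be assessed using the" ACCEPT instrument. The synopsis (Section 1.2) agrees, for example "Change from Baseline (Day 1) in treatment acceptance at Week 24, Week 48 and Week 152 (or Withdrawal". None of these entries limits the phase or time of the withdrawal.

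Collection is governed by footnote u to the Q4W Time and Events Table (Section 7.1.1) and footnote vv to the Q8W table (Section 7.1.2). During the Maintenance Phase, HAT-QoL, HIVTSQs, HIVTSQc, ACCEPT, PIN and the preference questionnaire are given "at W48 or upon Withdrawal only if occurring at or prior to Week 48". During the Extension Phase, HIVTSQs, ACCEPT, PIN and the oral-bridging preference questionnaire are given "at W152 or upon Withdrawal only if occurring at or prior to Week 152". Section 4.2.2 fixes the boundary between the phases: "Maintenance Phase (Day 1 up to Week 100".

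**The concern.** The endpoint tables and the schedule do not match. Someone who withdraws at Week 60 or Week 92 attends a withdrawal visit, but under the footnotes is not given HIVTSQs, ACCEPT or PIN. Someone who withdraws at Week 104 is given all three. No reason is stated for the difference.

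The instruments measure satisfaction, acceptance and the experience of injections, and Section 5.5 lists intolerability of injections among the reasons for stopping treatment. A value taken at withdrawal is the one most likely to reflect such a reason. For the affected participants the last recorded value dates from Week 48, before whatever led them to leave. An analysis plan can choose how to treat missing values, but it cannot recover questionnaires that the schedule never asked sites to administer.

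**Working it through.** The plan states no figure for this point, so the check is a comparison of texts followed by a range under a stated assumption.

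**Step 1: which instruments have a Week 152 endpoint.** HIVTSQs, ACCEPT and PIN do (Sections 1.2 and 3). HAT-QoL is assessed at Weeks 24 and 48, HIVTSQc at Week 48, and the general preference questionnaire at Week 48. For those three the Week 48 cut-off agrees with the endpoint.

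**Step 2: what is collected at withdrawal for HIVTSQs, ACCEPT and PIN.**

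| Time of withdrawal | Endpoint table | Footnotes u and vv |
|---|---|---|
| Maintenance Phase, up to Week 48 | withdrawal value called for | collected |
| Maintenance Phase, after Week 48 to Week 100 | withdrawal value called for | not collected |
| Extension Phase, up to Week 152 | withdrawal value called for | collected |

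The uncovered window is 100 − 48 = 52 weeks, or 52/152 = 34% of the follow-up to Week 152.

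**Step 3: what these leavers still contribute.** If on study at the time, they have HIVTSQs and ACCEPT at Day 1, Week 24 and Week 48, and PIN at Weeks 8, 24 and 48. Only the value feeding the Week 152 endpoint is absent.

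**Step 4: a neighbouring group.** Under Sections 4.2.3 and 5.6, a participant may finish at Week 100, decline the Extension Phase and count as a completer. Section 5.5 adds that a withdrawal visit coinciding with Week 100 is recorded as the Week 100 visit. These participants also have no questionnaire after Week 48.

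**Step 5: size.** The documents give no withdrawal rate for this window. With 1020 participants and an assumed fraction d leaving in it, the number without a withdrawal value is 1020 × d:

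- d = 1%: 10.2, about 10
- d = 3%: 30.6, about 31
- d = 5%: 51
- d = 10%: 102

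The completers in Step 4 would be additional; their number is also unknown.

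**The case against.** The rule may be deliberate. Each phase is paired with one main questionnaire time, Week 48 for Maintenance and Week 152 for Extension, and other withdrawal assessments are also limited by timing. A value from Week 56 entered into a Week 152 endpoint would be 96 weeks early, so leaving it out is defensible. This stands as a reason why either rule could be chosen. It does not reconcile the two texts: if the limit is intended, the endpoint tables should say so.

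The reason for leaving is also recorded elsewhere. Section 5.5 requires it on the case report form, and injection site reactions are assessed throughout. That softens the loss but does not supply the scores that define the endpoints.

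A reader might infer that these leavers drop out of the satisfaction, acceptance and injection-perception results altogether. They do not, as Step 3 shows. Whether they leave the Week 152 analysis depends on missing-data rules, and Sections 7.8 and 9.3.7 were not among the pages at hand. Nor are all questionnaires barred: footnotes x and yy give the oral-bridging preference questionnaire at a withdrawal visit up to Week 152, including after bridging in the Maintenance Phase.

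A reader might also infer a large imbalance between the arms from the phase 2b study in Table 4. There, participants counted as neither virologic success nor failure rose between Weeks 48 and 96 from 115 − 105 − 1 = 9 to 115 − 100 − 0 = 15 on Q4W, and from 115 − 106 − 8 = 1 to 115 − 108 − 5 = 2 on Q8W. Scaled to 510 per arm, 6/115 and 1/115 give about 27 and 4. The documents do not support that use:

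- The category is a Snapshot outcome, not a count of withdrawals. Section 2.2 places a Q8W participant who withdrew over intolerable injections among the virologic nonresponders.
- The figures are net changes of 6 and 1.
- Section 2.2 reports only one further adverse event leading to withdrawal after Week 48, across all arms.

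**Conclusion.** The inconsistency is real and stands in both schedules. For HIVTSQs, ACCEPT and PIN, the endpoint tables ask for a withdrawal value that the footnotes do not collect for Maintenance Phase withdrawals after Week 48 and up to Week 100. The range of about 10 to 102 participants rests only on the assumption that 1% to 10% of 1020 leave in that window. Neither the true number nor its split by arm can be found in the documents, so the direction and size of any bias in the Q8W versus Q4W comparison are unknown. The effect is confined to the Week 152 values of three secondary patient-reported endpoints. The primary and key secondary efficacy endpoints and the Week 24 and Week 48 questionnaire results are untouched. It should still be corrected, because the remedy is cheap and uncollected values cannot be recovered later.

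**What to change.** In footnotes u and vv, replace the phase-specific limits for HIVTSQs, ACCEPT and PIN with one rule: administer them at the withdrawal visit for any withdrawal up to and including Week 152, in either phase. Leave HAT-QoL, HIVTSQc and the Week 48 preference questionnaire at the Week 48 limit, since their endpoints end there.

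For participants whose window has already passed, collection is no longer possible. In that case, restrict the withdrawal alternative at Week 152 in Sections 1.2 and 3 to Extension Phase withdrawals, so that the stated endpoint matches what is collected.

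The same edit should cover participants who complete at Week 100 and decline the Extension Phase: either give them the three instruments at that last visit, or state that they have no Week 152 value.

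The cost is an edit to two footnotes (or to the endpoint tables) in an amendment, and three short paper questionnaires at a visit that already takes place.

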## 7.2. Screening and Critical Baseline Assessments

Written informed consent must be obtained from each potentially eligible participant by study site personnel prior to the initiation of any Screening procedures as outlined in this protocol. The consent form must have been approved by the Institutional Review Board (IRB)/Independent Ethics Committee (IEC). After signing an informed consent, participants will complete Screening assessments to determine participant eligibility. Each participant being screened for study enrolment evaluation will be assigned a participant number at the Screening visit. This number will be given sequentially in chronological order of participant presentation according to a numeric roster provided by GSK.

### 7.2.1. Screening Assessments

Eligibility criteria must be carefully assessed at the Screening visit. Physical examinations should be conducted as part of normal routine clinical care. Background information to be collected at Screening includes demography and prior ART history.

Eligible participants may be randomly assigned immediately as soon as all Screening assessments are complete and the results are available and documented. All participants will complete the screening period of approximately 14 days prior to Baseline (Day 1) during which all clinical and laboratory assessments of eligibility must be performed and reviewed. The Screening period may be extended to 35 days to accommodate availability of all Screening assessment results, completion of source document verification to satisfy the Inclusion and Exclusion Criteria, and scheduling. All Screening results **must** be available prior to randomization.

**All information about the participant's current regimen must be available for review by the Principal Investigator or designee prior to randomization. Source documents from other medical facilities must be located/received during the 14 day (up to 35 days) screening period and under no circumstances may the participant be randomized in the absence of source documentation even if there are delays in receipt of this information.**

Any available prior genotypic resistance testing must be provided to GSK, after screening and before randomization according to guidance in the SPM, to provide direct evidence of no pre-existing exclusionary resistance mutations. The lack of exclusionary resistance mutations must be confirmed by the study virologist, which will be provided before the screening window closes. Details on use of RAMOS for tracking historic resistance report availability and submission to ViiV Healthcare Virology for evaluation are described in the SPM. Details regarding baseline or prior resistance data must be noted in the source documentation.

Participants infected with HBV will not be enrolled in the study. Evidence of HBV infection is based on the results of testing at Screening for hepatitis B surface antigen (HBsAg), hepatitis B core antibody (anti-HBc), hepatitis B surface antibody (anti-HBs), and HBV DNA. HBV DNA will only be performed for participants with positive anti-HBc and negative HBsAg and negative anti-HBs (past and/or current evidence).

Participants with an anticipated need for HCV therapy during the study must not be enrolled into this study, as HCV therapy currently includes the prohibited medication interferon. The length of this study should be considered when assessing the potential need for therapy.

All participants will be screened for syphilis. Participants with untreated syphilis infection, defined as a positive RPR without clear documentation of treatment, are excluded. Participants with a serofast RPR result despite history of adequate therapy and no evidence of re-exposure may enrol after consultation with the Medical Monitor. Participants with a positive RPR test who have not been treated may be rescreened at least 30 days after completion of antibiotic treatment for syphilis.

The eCSSRS (see Section 7.4.6) assessed at the Screening visit will assess the participant's lifetime risk (any suicidal ideation, behavior, etc. occurring over the participant's lifetime). A positive alert (indicating some risk) is not necessarily exclusionary, rather a means to assess overall risk.

Participants who meet all entry criteria are randomized and assigned a randomization number. A single repeat of a procedure/lab parameter is allowed to determine eligibility (unless otherwise specified). Participants not meeting all inclusion and exclusion criteria at initial screen may be rescreened and receive a new participant number one time unless they were excluded for reason of having exclusionary historic genotypic resistance. Participants who are randomized into the trial and subsequently withdrawn from the study for any reason may not be rescreened.

### **7.2.2. Baseline Assessments**

At Day 1 and prior to randomization, any changes to the eligibility parameters must be assessed and any results required prior to randomization (e.g., Day 1 urine pregnancy test for women of childbearing potential) must be available and reviewed. The following demographic parameters will be captured: year of birth, sex, race and ethnicity. Medical/medication/family history will be assessed as related to the inclusion/exclusion criteria listed in Section 5.

HIV-1 genotypic resistance testing and plasma HIV-1 RNA measurement results from Screening must be available prior to the Baseline visit.

Baseline information to be collected at Day 1 includes general medical history and current medical conditions. Laboratory and health outcomes assessments will also be assessed. Questionnaire/surveys are recommended to be administered at the beginning of the visit before any other assessments are conducted, in the order specified. For participants who agree to the optional assessment, a whole blood sample for genetic research should be collected at Day 1 (if not already collected during participation in the ATLAS study).

In addition to a full routine medical history at Baseline, more detailed information will be collected for some disease processes such as:

- Cardiovascular medical history/risk factors (as detailed in the eCRF) will be assessed at Baseline and assessments will include height, weight, blood pressure, smoking status and history, pertinent medical conditions (e.g., hypertension, diabetes mellitus), and family history of premature cardiovascular disease. In addition, medical history/risk factors for renal disease such as nephropathy, renal failure, and nephrolithiasis will be assessed.
- history of illicit drug use [e.g., cocaine, heroin, and methamphetamine use];
- intravenous drug use history;
- gastrointestinal disease (e.g., GI bleeding, PUD, etc.);
- metabolic (e.g., Type I or II diabetes mellitus);
- psychiatric (e.g., depression);
- renal (e.g., nephrolithiasis, nephropathy, renal failure); and,
- neurologic disorders

Procedures conducted as part of the participant's routine clinical management [e.g., laboratory assessments] and obtained prior to signing of informed consent may be utilized for Screening or baseline purposes provided the procedure meets the protocol-defined criteria and has been performed in the timeframe of the study. Where possible local lab results should be confirmed by submission of samples to the central lab.

### **7.3. Efficacy**

#### **7.3.1. Plasma HIV-1 RNA**

Plasma for quantitative HIV-1 RNA will be collected according to the Time and Events schedule (Section 7.1). Methods to be used may include but are not limited to the Abbott RealTime HIV-1 Assay lower limit of detection (LLOD) 40 c/mL. In some cases, (e.g., where the HIV-1 RNA is below the lower limit of detection for a given assay) additional exploratory methods will be used to further characterize HIV-1 RNA levels.

#### **7.3.2. Lymphocyte Subsets, CD4+ and CD8+**

Lymphocyte subsets will be collected for assessment by flow cytometry (total lymphocyte counts, percentage and absolute CD4+ and CD8+ lymphocyte counts, ratios) according to Time and Events schedule (Section 7.1) and Laboratory Assessments (Section 7.4.2).

#### **7.3.3. HIV Associated Conditions**

HIV-associated conditions will be recorded as per Time and Events schedule (Section 7.1). HIV-associated conditions will be assessed according to the 2014 CDC Revised Classification System for HIV Infection (see Section 11.4).

## 7.4. Safety

### 7.4.1. Clinical Evaluations

The following clinical evaluations will be performed according to the Time and Events schedule:

- Monitoring and recording of all AEs and SAEs. Additional information on the Time Period and Frequency of Detecting AEs and SAEs is provided in Section 7.4.3.1.
- Physical exams should be conducted as part of normal routine clinical care. Abnormalities noted during any exam must be recorded in the eCRF (e.g., in the current medical conditions or AE logs).
- Height and weight will be measured and recorded. Height collected on the Day 1 (Baseline) only.
- Vital signs will include systolic and diastolic blood pressure and heart rate collected after resting for about 5 minutes. Temperature will also be collected.
- Past medical history, family history, social history, medication history. Targeted history on cardiovascular risk (smoking history, family and personal history).
- HIV-associated conditions will be recorded.
- Electrocardiogram: A 12-lead ECG will be performed in a semi-supine position after 5 minutes of rest. On Day 1 (Baseline) of the Maintenance Phase, ECGs should be performed in triplicate prior to first dose. An ECG machine that automatically calculates the heart rate and measures PR, QRS, QT, and QTc intervals is preferred, and these calculated numbers can be used for reporting purposes. Otherwise, an appropriately qualified ECG reader must interpret the results. The same interpreter should assess all ECGs for each participant for the site. Regardless, each ECG should be reviewed by a qualified ECG reader. The qualified ECG reader will make the non-calculated ECG interpretations. The same QT correction formula must be used for each individual participant to determine eligibility for and discontinuation from the study. This formula may not be changed or substituted once the participant has been enrolled.
- Regular monitoring of hematology, blood chemistry, urinalysis and fasting glucose and lipids (parameters to be tested listed below).
- Periodic assessment of glucose, insulin, and bone, cardiovascular, and renal markers;
- Pregnancy testing. A negative urine pregnancy test is required prior to initiation of IP, any dose of CAB LA or RPV LA or as required by the Medical Monitor following a treatment interruption(s). If serum testing is required locally, the results should be available prior to the visit where urine testing is indicated per the Time and Events Schedule (Section 7.1).
  - Participants who are enrolled in the study and have a positive pregnancy test during the course of the study, will be allowed to remain in the study,

provided a pregnancy specific ICF addendum is signed by the participant. No IP can be continued (oral or LA) in any pregnant participant until the benefit/risk assessment is discussed with the participant and the pregnancy specific ICF addendum has been signed. See details in [Appendix 11](#).

- Pregnant participants who remain in the study do not need pregnancy testing during the study, for the duration of their pregnancy.
- Evaluation and documentation of all concomitant medications and blood products.
- Injection Site Reactions (ISRs) will be assessed clinically during the Maintenance and Extension Phases for the following:  
Pain, tenderness, pruritis, warmth, bruising, discoloration, infections, rash, erythema, swelling, induration, and nodules (granulomas or cysts).
- A clinical assessment (using Division of Acquired Immunodeficiency Syndrome [DAIDS] grading scale) should be performed both before and after an injection to identify resolving and new ISRs. All injection site reactions are considered adverse events. The clinical assessment and interpretation of any ISR, will be documented in the ISR AE eCRF.
- Columbia Suicide Severity Rating Scale (eC-SSRS) will be assessed as per the Time and Events Schedule (see Section [7.1](#) and Suicidal Risk Monitoring Section [7.4.6](#)).

Any appropriately qualified site personnel (e.g., Investigator, sub-Investigator, or study coordinator/nurse) can perform assessments.

